### 10.3 Screening

The screening data for all subjects who are screened, but do not meet eligibility criteria, will not be analyzed or tabulated nor collected on the CRFs.

### 10.4 Subject Characteristics

The number of subjects included in the safety and/or effectiveness evaluations, subjects completing the study, and the reasons for any withdrawals will be tabulated by counts and percents. Continuous demographic data will be summarized using descriptive statistics. Categorical demographic data will be summarized using counts and percents. Abnormal medical histories and prior/concurrent medications obtained on the screening visit will be presented in data line listings.

### 10.5 Efficacy Criteria

**Scheduled Exam Intervals:** The change in received power ( $P_R$ ) measured by the SENSE device will be calculated and the accuracy of the SENSE algorithm will be tested for the SENSE measurements that correspond with the first, 12 hour, and 72 hour CT scans; and  $P_R$  will be compared to the hemorrhage volume on the corresponding CT scan. The change in  $P_R$  and CT hemorrhage volumes from the first study CT to 12 hours and from 12 hours to 72 hours will also be evaluated. Data will be summarized using descriptive statistics.

**Unscheduled CT Scans:** For any unscheduled CT scan that has a corresponding SENSE measurement, the SENSE  $P_R$  will be calculated and the accuracy of the SENSE algorithm will be tested; and the comparison to the hemorrhage volumes on the corresponding CT scan will be evaluated.

Although the sample size is small, the sensitivity and specificity of the  $P_R$  for monitoring changes in ICH will be estimated and evaluated for suitability as an outcome measure for determining the sample size for the pivotal study design.

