Main Results: In these experiments, the SENSE 9-antenna array device was able to detect blood in different areas of the brain, at varying volumes.

*Adverse Events in the Preclinical Study of the 9-antenna SENSE Device*

No adverse events were observed in any of the preclinical SENSE studies. In the 9-antenna *in vivo* study, an MRI was performed on each pig to assess whether continuous scanning with the SENSE device caused issues such as increased bleeding, tissue damage indicative of heating or otherwise. No evidence of tissue damage was apparent on MRI, nor were there signs of injury in the slices of pig brain after sacrifice. Additionally, 2,3,5-Triphenyltetrazolium chloride (TTC ) staining was performed in one pig and there were no adverse effects on tissues other than staining at the location of the ICH, including those in which an MRI were performed on the pigs with no negative findings.

*Preliminary Functionality of the 9-antenna SENSE Device*

Using data from the *in vivo* SENSE experiments on 8 pigs, we developed a preliminary SENSE algorithm for determining ICH volume and to estimate the sensitivity of the device. The algorithm gathers the received power from all of the antennae and characterizes the changes observed in the signal over time to determine a location and

size of the hemorrhage. Furthermore, it incorporates antenna distance, angle, and beam profile to create a weighted response with changes in the signal observed by certain antennae being more important than other antennae depending on the location within the head being monitored. The algorithm also accounts for different changes in the signal over time such as absolute difference, percent difference, standard deviation, positive versus negative change, and coefficient of variance.

Using the current setup in the pig *in vivo* experiments described above, the algorithm was able to determine the location of all hemorrhages and was able to detect changes in signal due to as little as 1 mL of blood infused into the brain. Furthermore, system drift, which is defined as change of signal over time due to variance in the system or natural physiological changes, was studied during control measurements, and by setting a limit above the maximum drift observed, the algorithm could still detect and localize all hemorrhages studied.

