## **6.0 Endpoints**

The primary endpoint for this early feasibility study is the correlation of the SENSE signal with CT changes over time.

Secondary endpoints will include the ability to process collected data in a manner that allows application and use of the SENSE device in a clinical environment and a preliminary estimate of the safety of the device when used in a clinical setting. Serious, unexpected adverse events will be recorded. Epileptic seizures will be an adverse event of special interest and recorded regardless of serious or unexpected status.

Qualitative information regarding device tolerability and compatibility with ICU workflow will be obtained from study subjects and ICU staff.

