#### 9.4 CT Scan Procedures

Study eligibility intracranial hemorrhage volume will be estimated by clinical and/or research staff using the ABC method. Subsequently, intracranial hemorrhage and edema volumes will be determined by a neuro-radiologist blinded to clinical data and SENSE device data. Quantification of volumes will be performed using computer-assisted methods. The blinded evaluator will be required to place seed-points within the volume of interest and adjust lower and upper intensity Hounsfield unit (HU) thresholds until the entire volume is correctly selected. In cases where the ICH volume cannot be differentiated from intraventricular hemorrhage (IVH) volume, the blinded evaluator will use freehand drawing tools in order to remove the IVH volume using his/her best

---

estimate. In this situation, the IVH will be determined using the original over-segmented volume that includes the combined ICH and IVH volumes,  $V_{total}$ , as  $IVH = V_{total} - ICH$ . This limitation is unavoidable as IVH has the same intensity as ICH and the two volumes often border each another. The volume (mL) and the affected part(s) of the brain will be measured from the segmented volume. Based on prior experimentation, it is anticipated there will be more difficulties in segmenting edema volumes as edema has more subtle HU intensity differences relative to normal tissue. Thus, edema segmentation will likely require more blinded evaluator effort (i.e., seed-points, freehand tools, etc.) The radiology report will be filed in the source documents for the study.

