### 9.5.2 Study Evaluations

The following study procedures will be performed at each of the following time points. If it is not possible to perform a measurement or examination due to the subject's condition or other reasons, the reason for not performing the test or measurement should be documented on the source documents.

- **Baseline:**

- A **first** study head CT will be performed on every study subject immediately prior to initiation of SENSE device monitoring.
- NIH Stroke Scale
- Glasgow Coma Scale
- SENSE device measurements within 15 minutes of **first study** head CT

- scan, or as soon as practicable
- Adverse event assessment
- **12 Hours (±6 hours):**
  - A standard of care head CT will be performed at 12 (±6) hours from first study CT to evaluate for hemorrhage expansion
  - NIH Stroke Scale
  - Glasgow Coma Scale
  - SENSE device measurements within 15 minutes of head CT scan, or as soon as practicable for continuous monitoring, or every 6 (±1) hours for intermittent monitoring
  - Adverse event assessment
- **72 Hours (±12 hours):** A study CT will be performed at 72 (±12) hours to evaluate cerebral edema.
  - NIH Stroke Scale
  - Glasgow Coma Scale
  - SENSE device measurements within 15 minutes of before or after head CT scan, or as soon as practicable
  - Adverse event assessment
- **7 days:** Adverse event assessment. After the subject is discharged from the hospital or through 7 days of hospital stay (whichever occurs first), the subject's inpatient medical records will be reviewed to detect any device related adverse events or epileptic seizures that may have emerged after the SENSE headset was removed.
- **6 weeks (±2 weeks):** A phone call with the patient or surrogate will be completed at 6 (±12) weeks to capture the presence or absence of adverse events that may have emerged after completion of the 72-hour SENSE device measurement period.

Changes from the screening or baseline medical history and concomitant medications should be recorded in the source documents. Changes that could affect the SENSE measurements or CT results should be recorded on the case report forms (CRFs), including head movements that may affect positioning of the SENSE device.

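### Section 10.5 compares P_R only with hemorrhage volume and leaves out the blinded edema volumes, so 72 h signal changes and 12–72 h false positives cannot be attributed to blood or edema

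*Combined protocol and SAP*

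**What the plan says.** Section 6.0 defines the primary endpoint as "the correlation of the SENSE signal with CT changes over time". That wording does not restrict the CT changes to hemorrhage.

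Section 9.5.2 gives the last scheduled scan a purpose of its own: "A study CT will be performed at 72 (±12) hours to evaluate cerebral edema". Sections 7.0 and 9.2 say the same. Section 9.4 states that "intracranial hemorrhage and edema volumes will be determined by a neuro-radiologist blinded to clinical data and SENSE device data", and warns that edema will be harder to segment than blood.

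Section 10.5 is the only specific efficacy analysis, because Section 10.0 says no detailed SAP will be written. At the first, 12 h and 72 h scans P_R "will be compared to the hemorrhage volume on the corresponding CT scan". The change in P_R and in "CT hemorrhage volumes from the first study CT to 12 hours and from 12 hours to 72 hours will also be evaluated". Unscheduled scans are also compared on hemorrhage volume. Finally, the sensitivity and specificity of P_R "for monitoring changes in ICH will be estimated and evaluated for suitability as an outcome measure for determining the sample size" of the pivotal study. Edema is not mentioned anywhere in Section 10.

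**The concern.** The device reads RF absorption across the skull and brain (Section 3.1), which as described is not specific to blood. Section 2.1 acknowledges "system drift, which is defined as change of signal over time due to variance in the system or natural physiological changes", and says that this drift "was studied during control measurements, and by setting a limit above the maximum drift observed". Those were pig experiments in which the device ran for 6 to 8 hours, and Section 2.1 reports no test of edema on P_R. The human 12–72 h interval is nominally 60 hours, or 60/8 = 7.5 to 60/6 = 10 times as long.

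If edema does move the signal, a P_R change at 72 h could reflect blood, edema or both, and the stated analysis sets it against blood only. The results are meant to refine the algorithm and to judge whether sensitivity and specificity can size the pivotal study (Sections 5.0 and 10.5). A signal credited to the wrong cause would carry into both uses.

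**Working it through.** The plan has no figure to reproduce: it states no target correlation, power or effect size. The check has four parts.

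**1. What can be attributed.** Write H for hemorrhage volume and E for edema volume, and suppose P_R = a·H + b·E + noise. The documents give neither a nor b.

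- Level comparison at 72 h: the slope of P_R on H alone is a + b·λ, where λ is the slope of E on H across subjects. A device that sees only blood (b = 0) gives a; one that sees only edema (a = 0) gives b·λ. Without E in the analysis the two cannot be told apart. If edema is unrelated to bleed size (λ = 0), edema adds scatter and no spurious slope.
- 12–72 h change: ΔP_R = a·ΔH + b·ΔE + noise. If the hemorrhage is stable, ΔH is near 0 and any signal is b·ΔE plus noise. The cause of an alarm is then visible only if ΔE is shown.

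**2. How far the stated change comparisons are affected.** All inputs here are assumptions:

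- 10 subjects; first-CT hemorrhage lognormal, median 15 mL, log-SD 0.8, limited to 3–90 mL.
- 30% of bleeds expand by 33–100% by 12 h and none later; other hemorrhage change has SD 0.5 mL.
- 12–72 h edema growth is k times the 12 h hemorrhage volume (mean k = 0.5, CV 50%), with one fifth of that in the first interval.
- Noise SD is 3 mL-equivalents of blood per interval.

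Median correlation of ΔP_R with ΔH, by interval as 10.5 lists them:

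| Device | First CT to 12 h | 12 h to 72 h |
|---|---|---|
| Blood only (a = 1, b = 0) | 0.92 | 0.17 |
| Blood plus edema (a = 1; b = 0.25, 0.5, 1) | 0.91 to 0.93 | low |
| Edema only (a = 0; b = 0.25, 0.5, 1) | 0.09, 0.16, about 0.26 | about 0 |

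With twice the edema growth (k = 1.0) and b = 1, the first-interval values are 0.89 with a blood response and 0.35 without one. The first interval therefore separates the devices with little disturbance. The second carries little hemorrhage signal even without edema, because the model assumes no late growth.

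**3. Where false positives would fall.** Assume each subject contributes two intervals to specificity (10.5 does not fix the unit) and 3 of 10 bleeds grow, all by 12 h. No-growth intervals number 20 − 3 = 17, and 10/17 = 59% of them are 12–72 h intervals (10/18 = 56% with 2 growers; 10/16 = 62.5% with 4). Each false alarm costs 1/17 = 5.9 points of specificity.

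**4. What an edema adjustment could show.** A partial correlation with one covariate and 10 subjects has 10 − 3 = 7 degrees of freedom. When the true value is 0, its 95th percentile is 1.895/√(7 + 1.895²) = 0.58. Simulation gives a 5th-to-95th percentile range of −0.58 to 0.57.

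**The case against.** The strongest reply is that the study already provides for this. Sections 3.3 and 9.3 foresee correlating SENSE data with clinical and imaging data, Section 10.0 promises descriptive tabulation, and 10.5 already keeps the two intervals apart. Hemorrhage is also the natural comparator, since the objectives in 5.0 concern intracranial hemorrhage. The study has up to 10 subjects and no success criteria (10.8), and its output never reaches clinical care. All of that stands and keeps the stakes low. The general sentences do not, however, commit anyone to set edema beside P_R.

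A reader might go further and infer that edema creates or hides the primary correlation. The documents do not support this:

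- A large weakening appears in the assumed model if the two intervals are pooled (0.85 falling to 0.37 at b = 1), but 10.5 describes no pooling.
- A strong spurious correlation appears if change in P_R is set against the level of hemorrhage at 72 h, but 10.5 compares P_R with volume and, separately, change with change.

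Neither figure is evidence of bias in the stated analysis. The model also treats P_R as a single number, whereas the algorithm in Section 2.1 weights antennas and uses the direction of change.

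Nor is the specificity wrong. An alarm caused by edema is still a false positive for hemorrhage, and listing its likely cause does not alter the estimate.

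**Conclusion.** The point holds as a cheap improvement. Section 10.5 names no use for a blinded measurement that the protocol collects and gives as the purpose of the 72 h scan. If edema affects P_R, the 72 h level comparison and the 12–72 h changes or false positives cannot be assigned to blood or edema from the stated analysis. The first-CT-to-12 h change comparison is little affected under the assumed model.

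Whether edema moves P_R at all, in which direction, and how edema scales with bleed size are not in the documents. The size of any distortion is therefore unknown. What is gained is clearer reading of the 72 h data and of the causes of false positives; a bias in the primary correlation has not been shown.

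**What to change.** Add to Section 10.5, labelled descriptive:

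- At each scheduled and unscheduled CT, P_R will be compared with blinded edema volume as well as hemorrhage volume.
- Change in P_R will be compared with edema change as well as hemorrhage change, separately for first CT to 12 h and for 12 h to 72 h, without pooling.
- Changes in P_R, hemorrhage and edema will be listed per subject and interval. Each false positive will be shown with the edema change in that interval.
- Any edema-adjusted correlation will be exploratory.

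The cost is a few sentences and one listing from volumes already planned. There are two limits. Edema is harder to segment (9.4), so any adjustment is partial. With 10 subjects an adjusted correlation can flag edema as a possible explanation but cannot settle it.

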### 10.6 Safety Criteria -- Adverse Events

The presence or absence of AEs and device malfunctions captured on the forced choice Complications/Adverse Events CRF and all other device related adverse events will be tabulated and summarized.

Seizures will be recorded and tabulated regardless of serious or unexpected status.

## **10.7 Other Outcome Measures**

Qualitative and human factors information regarding device tolerability and compatibility with ICU work-flow obtained from study subjects and ICU staff will be summarized.

## **10.8 Study Success**

This first-in-man study is not designed or powered to achieve pre-specified success or failure criteria.

## **10.9 Dropouts/Lost-to-Follow-up**

Subjects may drop out at any time during the study. Effectiveness data from dropouts will be included through the last recorded subject measurement, except in those instances where missing data preclude the analysis of serial or comparative data points.

All subjects who have a SENSE device placed on his/her head will be included in the safety analysis. All subjects that sign a consent form but do not get a device assigned to them will be replaced.

## **10.10 Interim Analysis**

Outcomes from the study may be tabulated to evaluate the progress of the study; however, an interim analysis will not be performed.

## **10.11 Poolability**

A poolability analysis will not be performed for this single-site study.

## **10.12 Missing data**

To assess the impact of missing data, a sensitivity analysis will be conducted. Under this analysis, the primary endpoints will be assessed in a worst case and best case scenario. For this study, the best case scenario is to use the last observation carried forward; and the worst case is to use the baseline value. Since the number of missing data points in this type of study is expected to be extremely small, it is anticipated that the sensitivity analysis will yield results similar to the main analysis.

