### 9.2 Examination Schedule

The following examination schedule will be followed from screening through 6 ( $\pm 2$ ) weeks post-enrollment:

- **Diagnosis:** CT Scan 1 – standard of care; diagnostic head CT scan within 24 hours of symptom onset.

- **First Study CT:** CT Scan 2 – study CT; first study CT scan as soon as practicable after informed consent, followed by SENSE monitoring. Place SENSE device on subject's head within 15 minutes of completion of the first CT scan or as soon as practicable, with continuous SENSE monitoring until the SENSE device is removed to perform the 12-hour CT scan. If there is a delay in obtaining the first study CT scan, SENSE monitoring may begin after informed consent and before the first study CT scan to capture possible HE.
- **12 Hours:** CT Scan 3 – standard of care; CT scan 12 ( $\pm 6$ ) hours after first study CT scan, followed by continuous or intermittent SENSE monitoring. For continuous SENSE monitoring, replace SENSE device on the subject's head within 15 minutes, or as soon as practicable, after completion of the 12-hour CT scan and obtain continuous SENSE measurements until the SENSE device is removed to perform the 72-hour CT scan. If continuous SENSE monitoring is temporarily suspended or for any reason (e.g., unscheduled CT scan, EEG, patient care), resume continuous monitoring as soon as practicable. For intermittent monitoring, the SENSE device will be placed on the patient for a minimum of 22 minutes every 6 ( $\pm 1$ ) hours until the 72-hour CT scan is obtained. A final SENSE measurement will be completed within 15 minutes before or after the 72-hour CT scan.
- **72 Hours:** CT Scan 4 – study CT; end of study CT scan 72 ( $\pm 12$ ) hours after first study CT scan.
- **Unscheduled:** Unscheduled CT scan(s) may be obtained as needed throughout the study per standard of care as warranted by the treating team. Any head CT performed for clinical deterioration as standard of care between the first and 72 hour study CTs will be collected and analyzed. If SENSE monitoring has been temporarily suspended or is being performed intermittently, obtain a SENSE measurement within 15 minutes before or after the unscheduled CT scan whenever practicable, following the procedures above.
- **6 weeks:** Phone call with patient or surrogate to capture the presence or absence any adverse events that may have emerged after completion of the 72-hour SENSE device measurement period.

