### 9.3 SENSE Device Monitoring Procedure

The device will be used according to the written Instructions for Use provided by the Sponsor. The device will emit and analyze signals of 40 seconds once every 10 minutes for up to a maximum of 72 ( $\pm 12$ ) hours, effectively minimizing the amount of RF radiation to which the subject is exposed while providing essentially continuous monitoring from a clinical point of view. This corresponds to a duty cycle (DC) of about 7%.

If the subject's condition is such that a SENSE device measurement cannot be obtained, the measurement may be omitted at the investigator's discretion; and the omission should be documented in the source documents.

The user interface requires the researcher to input the subject ID and headset ID so that the results can be entered into a database either via upload or manually. The research personnel will also sync the headset with the control box. Once these steps are completed, the research personnel can activate the device by hitting "Start Monitoring." The software will provide error messages if any required fields are blank.

Once activated, the device scans the subject according to the schedule selected per protocol. Before each scan, the device will run a diagnostic to ensure that all components are functioning normally. Data will be collected after each scan for subsequent analysis and correlation with clinical and imaging data.

The processing control unit will store the results from each subject's scans in a file on the device. If the subject ID is changed, the device will start a new file.

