When the SENSE device is placed on the subject's head, two small ink dots will be marked on the head corresponding to a known location on the device to allow for the device to be removed and replaced consistently throughout testing. If the SENSE device is removed to perform the CT or SENSE monitoring is temporarily suspended for any reason (including whenever a routine EEG is performed) during continuous SENSE monitoring, the SENSE device will be replaced; and SENSE monitoring will resume within 15 minutes, or as soon as practicable, after each CT scan or other reason for suspension is finished. For intermittent SENSE monitoring, the SENSE device will be replaced and SENSE measurements obtained at 6 ( $\pm$ 1) hour intervals. A SENSE measurement obtained within 15 minutes ~~of before or after~~ each CT scan, or as soon as practicable thereafter, will be used for comparison with the corresponding CT scan for data analysis. The purpose of obtaining SENSE measurements at the same time as the CT scan is to compare the output from the SENSE device with the CT scans.

Subjects requiring continuous EEG monitoring or other care that precludes placement of the SENSE device will have SENSE monitoring discontinued; and the subject will be terminated from the study according to the procedures described in Section 9.10, Early Termination if SENSE monitoring cannot be resumed during the remainder of the study.

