### 9.5.3 Adverse Events and Device Malfunctions

Adverse events and device malfunctions will be assessed at study entry and at the baseline, 12 hour, 72 hour and 6 week evaluation time points. If it is anticipated that a subject will die or be taken for a neurosurgical procedure before the 12 hour CT scan, the scan will be performed earlier if practicable and used to judge hemorrhage. If it is anticipated that a subject will be discharged from the hospital, die, or undergo a neurosurgical procedure after the 12 hour CT scan but before the 72 hour scan, the 72 hour scan will be performed earlier if practicable and used for analysis.

During the 72 hours of monitoring, adverse events of particular interest for this first-in-man study in an ICU setting include:

- Adverse tissue reactions from the headset, such as skin irritation, abrasion or other dermatological effects
- Discomfort of the head or neck from the headset
- Seizures (defined as clinical tonic-clonic activity that occurs during the 72 hours of SENSE monitoring)

Device malfunctions will also be assessed for the SENSE device. Such malfunctions could include:

- Failure of the device to operate
- Operator errors
- Interference with other devices, including SENSE device interference with other monitors (e.g., ICP monitor dislodges) or other monitor (e.g., intraventricular catheter placement) interferes with SENSE device monitoring or headset placement

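### Section 10.12 labels LOCF the best case and the baseline value the worst case, but for a correlation endpoint neither rule is best or worst by construction

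*Combined protocol and SAP*

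**What the plan says.** Section 6.0 gives the primary endpoint as "the correlation of the SENSE signal with CT changes over time". It names no coefficient and no rule for pooling time points. Section 10.5 compares received power with hemorrhage volume at the first, 12-hour and 72-hour CTs, and adds that changes "from the first study CT to 12 hours and from 12 hours to 72 hours will also be evaluated".

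Section 10.12 applies two scenarios to the primary endpoints: "the best case scenario is to use the last observation carried forward; and the worst case is to use the baseline value". It expects results close to the main analysis because "the number of missing data points in this type of study is expected to be extremely small", and gives no number. It does not say whether SENSE, CT or both are filled in, or what counts as the last observation.

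Other sections bear on how gaps arise:
- Section 9.3 says that, if the subject's condition prevents a SENSE reading, "the measurement may be omitted at the investigator's discretion". It also says: "Subjects requiring continuous EEG monitoring or other care that precludes placement of the SENSE device will have SENSE monitoring discontinued".
- Section 9.5.3 covers expected discharge, death or neurosurgery after the 12-hour scan: "the 72 hour scan will be performed earlier if practicable and used for analysis". Sections 9.9 and 9.10 ask for a final CT and SENSE measurement where practicable.
- Section 9.2 says CTs done for clinical deterioration "between the first and 72 hour study CTs will be collected and analyzed".
- Section 10.9 uses dropouts' effectiveness data up to their last recorded measurement.

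**The concern.** Best-case and worst-case labels suit an outcome where a larger value is better for the device. A correlation has no such direction: a filled-in value raises or lowers r according to where its point falls among the others. A report that follows Section 10.12 exactly could print a worst-case r above the best-case r, or print two values that both lie on one side of the result that complete data would have given.

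The likely reader is whoever plans the pivotal study, since Sections 5.0 and 10.1 give the estimates that purpose. Section 10.0 says that no detailed SAP will follow, so nothing later would correct the labels.

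**Working it through.** The plan states no figure on this point, so there is none to reproduce. It also gives no coefficient, SD or missing-data rate. The check therefore assumes Pearson's r and uses invented data.

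**Step 1. What each rule inserts.** Let x be CT volume and y the SENSE signal at 0, 12 and 72 hours. If the 72-hour pair is missing, the 12–72 h change becomes:
- LOCF: (x12 − x12, y12 − y12) = (0, 0).
- Baseline value: (x0 − x12, y0 − y12), the subject's own 0–12 h change with both signs reversed.

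The reversed point lies on the line through the origin and the subject's 0–12 h change, so it can strengthen r.

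**Step 2. Example on the interval-change scale.** Five subjects, (CT, SENSE) changes:
- 0–12 h: (6,5) (2,3) (1,1) (3,2) (0,1)
- 12–72 h: (2,1) (0,1) (1,0) (−1,0) (1,2)

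The intervals are pooled, and r = (Σxy − ΣxΣy/n) / √[(Σx² − (Σx)²/n)(Σy² − (Σy)²/n)]. The first subject's 72-hour data are then removed.

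| Case | Point used | r |
|---|---|---|
| Complete | (2,1) | (47 − 24)/√(34.5 × 20.4) = 0.867 |
| Observed pairs, n = 9 | none | 23.33/√(34.22 × 20) = 0.892 |
| Pair missing, LOCF | (0,0) | (45 − 19.5)/√(36.1 × 22.5) = 0.895 |
| Pair missing, baseline | (−6,−5) | (75 − 7)/√(84.1 × 60) = 0.957 |
| SENSE missing, LOCF | (2,0) | (45 − 22.5)/√(34.5 × 22.5) = 0.808 |
| SENSE missing, baseline | (2,−5) | (35 − 15)/√(34.5 × 60) = 0.440 |

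With the pair missing, the worst case is the highest value in the table. With only SENSE missing, both rules fall below the complete-data 0.867.

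**Step 3. Same data as change from baseline.** The 72-hour points become (8,6) (2,4) (2,1) (2,2) (1,3).

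| Case | Point used | r |
|---|---|---|
| Complete | (8,6) | (108 − 75.6)/√(54.1 × 27.6) = 0.838 |
| Pair missing, LOCF | (6,5) | (90 − 67.5)/√(36.5 × 22.1) = 0.792 |
| Pair missing, baseline | (0,0) | (60 − 41.8)/√(26.9 × 21.6) = 0.755 |
| SENSE missing, LOCF | (8,5) | (100 − 72.9)/√(54.1 × 22.1) = 0.784 |
| SENSE missing, baseline | (8,0) | (60 − 59.4)/√(54.1 × 21.6) = 0.018 |

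Here the order matches the labels, although all four filled-in values still lie below the complete-data 0.838.

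**Step 4. A missing 12-hour value.** If only scheduled CT-paired values count as observations, the last one before 12 hours is the baseline, so both rules give the same number.

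**Step 5. How often, under assumed inputs.** Simulation of 10 subjects with bivariate normal changes (SD 1), pooled intervals, five patterns of mean change, true r of 0, 0.5 or 0.8, and 72-hour values missing for random subjects (60 settings, 3,000 trials each):

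| | One missing | Three missing |
|---|---|---|
| Worst above best, pair missing | 50–81% | 50–94% |
| Worst above best, SENSE only | 25–59% | 15–65% |
| Complete-data r between the two | 21–36% | 14–35% |

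The high pair figures need net early growth; with zero mean change the figure is about 50%. With one value missing, the median shift from the observed r is small: 0.000–0.025 for LOCF and 0.006–0.10 for baseline. A separate simulation on other assumed data, using levels as well as changes, had the baseline rule higher in 25–53% of runs and the complete-data r outside the two values in 65–72%.

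**The case against.** The case for leaving the text alone has five parts.

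- **It is only wording in a sensitivity analysis.** The study is descriptive, Section 10.8 sets no success criterion, and Section 10.9 rests the main analysis on observed data. This stands and limits the impact. A reader might infer that the primary estimate itself is at risk; the documents do not support that.
- **Section 10.12 says scenario, not bound.** This stands. A reader might infer that the plan claims limits, but it does not. The labels invite that reading, which is a weaker charge.
- **The order depends on the scale.** This stands. A reader might infer that the labels are always reversed; Step 3 shows otherwise. It does not rescue the labels, because they hold on some data and scales and fail on others.
- **The 12-hour coincidence depends on a reading.** This stands. Section 9.3 has a SENSE scan every 10 minutes, and Section 10.9 speaks of the last recorded measurement. If interim scans or unscheduled CTs count, the two rules can differ.
- **Few values will be missing, and the SENSE-only error is conservative.** Partly stands. Early and final scans reduce gaps, and a small typical shift agrees with Section 10.12's expectation. But those scans depend on practicability, SENSE readings may be omitted, and a best case that tends to understate r is still mislabelled.

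**Conclusion.** The point holds as one of labelling and interpretation. Neither rule in Section 10.12 is best or worst for a correlation by construction, and the two values should not be read as limits on the effect of missing data. That conclusion rests on Step 1 and the counterexamples, not on the simulation.

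The impact is minor to modest. It is confined to a descriptive sensitivity analysis in up to 10 subjects, and one missing value usually moves r little. All data values, the Pearson coefficient and the pooling of intervals are assumptions; the main example and the 60-setting simulation apply to the interval-change scale. The change is still worth making: following the text exactly can yield mislabelled results, and the repair is cheap.

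**What to change.** In Section 10.12:

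1. Drop the words best case and worst case.
2. State that the main analysis uses observed CT–SENSE pairs, including the early or final scans of Sections 9.5.3, 9.9 and 9.10.
3. Keep LOCF and the baseline value only as two named, unlabelled single imputations. State whether SENSE, CT or both are filled in, and whether interim SENSE scans and unscheduled CTs count as the last observation.
4. Add the lowest and highest correlation found when each missing change is varied over a stated plausible interval. Keep the real CT value when only SENSE is missing. Use at least the observed minimum to maximum, and a wider interval when the reason for the gap (death, neurosurgery, care that precludes the headset) suggests an unusual change.

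The whole interval must be searched, not only its ends. In the Step 2 example with SENSE missing, the two ends give 0.777 and 0.808 and miss 0.867, while the full interval gives 0.777 to 0.893. With the pair missing it gives 0.464 to 0.929.

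Item 4 should be described as an illustrative range, not a bound. In the 60-setting simulation the observed-minimum-to-maximum version contained the complete-data r in 91–100% of trials, but only for values missing at random, under those assumed inputs and the pooled interval-change scale. In a rerun where the missing subject was the one with the largest CT change, SENSE-only coverage fell to about 74–91%.

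The cost is a few sentences and a short grid search. The downside is a wider, less favourable range. With true r 0.5 and mean changes of +1 then +0.5 SD, the average range is 0.25 to 0.60 for one missing pair (observed 0.52) and −0.07 to 0.71 for three.
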